7.5.1.2. Categorical Efficacy Endpoints

For the following categorical parameters, summary statistics, including sample size, frequency, and percentages, will be presented by visit for both cohorts.

- Proportion of participants achieving F-VASI50/75/90
- Proportion of participants achieving T-VASI50/75/90
- Proportion of participants achieving a VNS of "4 A lot less noticeable" or "5 No longer noticeable"

7.7. Pharmacokinetic Analyses

Plasma concentrations of ruxolitinib at all study visits will be summarized using descriptive statistics by cohort, treatment group, and/or visit.

Plasma ruxolitinib steady-state exposures ($C_{min,ss}$) will be derived as the average of all preapplication concentrations of ruxolitinib for each participant, and then descriptive summaries of $C_{min,ss}$ will be generated by cohort and treatment group.

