2.1.2. Clinical Pharmacokinetics

Clinical PK studies have demonstrated that exposures of ruxolitinib were generally strength-dependent with a moderate interparticipant variability. The systemic PK following topical application in treatment of plaque psoriasis (Study INCB 18424-202) and AD (Study INCB 18424-206) is characterized by apparent first-order release, modest peak-to-trough excursion (ratio ~2), estimated relative bioavailability of 3% to 5%, and an apparent terminal elimination half-life of approximately 3 days. The plasma metabolite profile following topical application is generally similar to that observed following oral administration.

Preliminary PK data are available from topical application in treatment of vitiligo (Study INCB 18424-211). Plasma ruxolitinib concentrations reached steady-state at or before Week 4 and were similar at Week 24/Week 28 after treatment of ruxolitinib cream. Plasma concentrations of ruxolitinib for predose and 2.0-hour postdose were similar, indicating a slow rate of absorption. Application of ruxolitinib cream 0.15% QD, 0.5% QD, 1.5% QD, and 1.5% BID resulted in mean (range) plasma concentrations of 5.75 nM (0-28.8 nM), 12.6 nM (0-82.1 nM), 59.1 nM (0-245 nM), and 113 nM (0-662 nM), respectively, after 24 weeks of treatment. Plasma concentrations increased as dose strength and frequency of dosing were increased.

The ruxolitinib terminal half-life following oral administration is approximately 3 hours with no appreciable accumulation of either parent or metabolites with BID oral dosing. However, the long apparent half-life (~4 days) observed in topical treatment is due to the slow absorption from the skin, which acts as a depot (Study INCB 18424-202). Therefore, the plasma concentration of ruxolitinib (following its topical application) reaches steady-state in 2 to 4 weeks and remains relatively unchanged after steady-state is reached, and this was confirmed in Study INCB 18424-203 and Study INCB 18424-211.

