6.7. Rescue Treatment

For participants in Cohort A, if there is a loss of clinically meaningful response on the face (ie, < F-VASI75) at any time, the participants will receive open-label ruxolitinib cream 1.5% BID until completing the study (ie, Week 104 or EOT).

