8.4. Pharmacokinetic Assessments

Venous blood samples will be collected to assess the PK of ruxolitinib cream in participants at each study visit indicated in Table 3.

The exact date and time of the PK blood draws and the date and time of the last application of study drug preceding the blood draw (if applicable) will be recorded in the eCRF.

Instructions for sample preparation and shipping will be provided in the Laboratory Manual. Participants will receive reminder cards in advance of the study visit providing instruction to hold the application of study drug on the day of the visit and a place to record the time of the prior dose of study drug.

Pharmacokinetic blood samples can be collected at any time prior to study drug application at the site at the Week 80 visit and at any time at the W104 (EOT) visit. Blood samples must not be drawn from the area that has been treated with study drug. If it is not possible to access an area that is not treated with study drug, the site must adequately document this in the eCRF and not take the PK blood sample for that visit. After the PK sample is drawn, participants will apply ruxolitinib cream 1.5% or vehicle cream at the site.

All analyses will be conducted by Incyte Corporation (Wilmington, DE) or Incyte's designee.

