10.4.3. Other Analyses

Pharmacokinetic endpoints are listed in Section 3. The ruxolitinib plasma concentration data collected at study visits will be analyzed using summary statistics. Pharmacokinetic steady state is achieved before Week 4 in vitiligo patients, and therefore all observed ruxolitinib plasma concentrations will be averaged to obtain an overall mean exposure for each participant.

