2.2. Study Objectives and Endpoints

Table 1 presents the endpoints and objectives.

Table 1: Objectives and Endpoints

| Objectives | Endpoints |
|---|--|
| Primary | • |
| To evaluate the duration of clinical response of ruxolitinib cream in participants with vitiligo. | For participants who are randomized in Cohort A: • Time to relapse (defined as < F-VASI75). |
| Key Secondary | |
| To evaluate the duration of clinical response of ruxolitinib cream in participants with vitiligo. | For participants who are randomized in Cohort A: • Time to maintain ≥ F-VASI90 response. |
| Secondary | |
| To further evaluate the efficacy of ruxolitinib cream. | Proportion of participants who achieve F-VASI50/75/90 during the extension treatment period. Actual measurements, change, and percentage change from baseline in F-VASI. Proportion of participants who achieve T-VASI50/75/90 during the extension treatment period. Actual measurements, change, and percentage change from baseline in T-VASI. Actual measurements, change, and percentage change from baseline in F-BSA. Actual measurements, change, and percentage change from baseline in T-BSA. Proportion of participants achieving a VNS of "4 – A lot less noticeable" or "5 – No longer noticeable" during the extension treatment period. |
| To determine the participants' quality of life. | Change from Week 52 in DLQI (or CDLQI) during the extension treatment period. |
| To evaluate the safety and tolerability of ruxolitinib cream. | The frequency and severity of AEs; includes performing physical examinations and collecting vital signs and laboratory data for hematology and serum chemistry. |
| To evaluate the ruxolitinib PK in plasma after treatment with ruxolitinib cream. | Trough plasma concentrations of ruxolitinib at Week 80 and Week 104. |

Table 1: Objectives and Endpoints (Continued)

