5.2. Treatment Groups

This is a double-blind, vehicle-controlled, randomized withdrawal and treatment extension study that will enroll eligible participants who have completed either Study INCB 18424-306 or Study INCB 18424-307 (parent studies). Data will be summarized based on the treatment regimen that was assigned at Week 52 (ITT-Ext) or that the participant actually applied (FAS).

For Cohort A, treatment groups are ruxolitinib cream 1.5% BID and vehicle cream for participants before open-label rescue treatment. For participants who cross over from vehicle cream to open-label ruxolitinib cream, the treatment group will be Vehicle-1.5% BID. For Cohort B, the treatment group will be based on the treatment assignment at Day 1 of the parent study (vehicle to 1.5% BID and 1.5% BID to 1.5% BID).

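### The per-participant Cmin,ss mixes vehicle-period and on-drug samples, so vehicle participants rescued between the Week 80 sample and Week 104 get about half their on-drug trough

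*SAP*

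**What the plan says.** SAP 7.7 makes two PK summaries. The first describes plasma concentrations at the study visits by cohort, treatment group and/or visit. The second is a derived steady-state exposure, Cmin,ss, which "will be derived as the average of all preapplication concentrations of ruxolitinib for each participant" and is then summarised by cohort and treatment group. Protocol 10.4.3 observes that steady state is reached before Week 4 in vitiligo and continues: "therefore all observed ruxolitinib plasma concentrations will be averaged to obtain an overall mean exposure for each participant".

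The listed PK endpoint is "Trough plasma concentrations of ruxolitinib at Week 80 and Week 104" (SAP 2.2). Those are the only two PK draws in the protocol's Schedule of Activities (Table 3).

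Cohort A participants randomised to vehicle stop ruxolitinib at Week 52. If facial response falls below F-VASI75 at any time, "the participants will receive open-label ruxolitinib cream 1.5% BID until completing the study" (Protocol 6.7). For reporting, SAP 5.2 says: "For participants who cross over from vehicle cream to open-label ruxolitinib cream, the treatment group will be Vehicle-1.5% BID".

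**The concern.** The reason for pooling samples is that concentrations stay level once steady state is reached. That holds under uninterrupted dosing. It does not hold for a participant who is on vehicle at one draw and on ruxolitinib at the next.

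The average is taken within participant before any grouping, so a later summary by treatment group cannot separate the two samples. The result would be labelled a ruxolitinib steady-state trough for the re-treated group, and the error always runs towards lower exposure. What is at stake is the reported exposure on re-treatment after withdrawal, a descriptive result.

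**Working it through.** The plan gives no figure to reproduce, so the rule is applied to the design.

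**Inputs**
- PK draws at Week 80 (predose) and Week 104 (Protocol Table 3).
- Apparent half-life after topical use of about 3 to 4 days, and 2 to 4 weeks to steady state (Protocol 2.1.2).
- Illustrative on-drug value C = 113 nM, the Phase 2 mean for 1.5% BID: "and 113 nM (0-662 nM), respectively, after 24 weeks of treatment" (Protocol 2.1.2).
- Share f of the Vehicle-1.5% BID group rescued after the Week 80 draw and before Week 104. The documents do not give it, so it is an assumption.

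**Step 1: drug remaining at Week 80 on vehicle.** Weeks 52 to 80 are 28 × 7 = 196 days. At a 4-day half-life this is 196/4 = 49 half-lives, and at 3 days 196/3 ≈ 65. The remaining fraction, 2^(−t/half-life), is at most about 2 × 10⁻¹⁵, which is effectively zero.

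**Step 2: concentration at Week 104.** The fraction of steady state reached is 1 − 2^(−t/half-life). At 14 days it is 0.91 to 0.96 and at 28 days above 0.99, which agrees with the protocol's 2 to 4 weeks.

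**Step 3: the participant's Cmin,ss, (Week 80 + Week 104)/2.**

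| Rescue starts | Days on drug by Week 104 | Cmin,ss as a fraction of steady state |
|---|---|---|
| Week 80 visit, after the draw | 168 | 0.50 |
| Week 92 visit | 84 | 0.50 |
| Unscheduled, 4 weeks before Week 104 | 28 | 0.50 |
| Unscheduled, 2 weeks before | 14 | 0.46 to 0.48 |
| Unscheduled, 1 week before | 7 | 0.35 to 0.40 |

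In the illustration, (0 + 113)/2 = 56.5 nM. In every row the average is half of the Week 104 sample itself, whatever that sample's value.

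**Step 4: the group mean.** Suppose the rest of the group has on-drug samples with mean C. The mean is then (1 − f)·C + f·C/2 = C·(1 − f/2).

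| Assumed f | Reported mean / on-drug mean | Understatement |
|---|---|---|
| 10% | 0.95 | 5% |
| 25% | 0.875 | 12.5% |
| 50% | 0.75 | 25% |

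**Step 5: who is not affected.** Rescue at a scheduled visit up to Week 68 leaves at least 12 weeks on drug before the Week 80 draw, so both samples are on-drug. The Cohort A ruxolitinib arm and Cohort B are assigned ruxolitinib throughout.

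**The case against.** **The groups can be read by period.** SAP 5.2 defines the two Cohort A groups as applying before rescue and names Vehicle-1.5% BID only after crossover. On that reading a Week 80 sample taken before rescue belongs to vehicle. This is a fair reading of SAP 5.2, but SAP 7.7 averages by participant and does not adopt it. Where the SAP wants a split it writes one: a cut at rescue for other secondary efficacy (7.5.1) and for laboratory tests and vital signs (8.1), and treatment-specific dates for adverse events (8.2.1). PK has none.

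**The pharmacokineticist reviews the records.** SAP 5.3.4 provides for this, but the review is worded to exclude participants, not single samples. Sample-level conventions may exist in the separate data displays; the documents do not show them.

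**The Week 104 sample may not count as preapplication.** Protocol 8.4 allows the draw "at the Week 80 visit and at any time at the W104 (EOT) visit". If that sample were left out, only the near-zero Week 80 value would remain, which is worse.

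**Stronger readings.** A reader might infer three things that the documents do not support.
- That reported exposure for the whole re-treated group is halved. That would require f = 100%.
- That the listed secondary endpoint is wrong. It is specific to visit, and a summary by visit averages nothing across visits.
- That samples before steady state are a general problem. Scheduled rescue visits fall at least 12 weeks before the next PK draw, so this arises only with an unscheduled rescue within about 4 weeks of a draw.

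These limits on scope stand.

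**Conclusion.** The point holds for the derived Cmin,ss only. As written, the rule gives a vehicle participant rescued between the Week 80 sample and Week 104 a value about half of the on-drug sample. This rests on the stated half-life and first-order decline, and does not depend on 113 nM. The 56.5 nM figure is not a prediction: the Phase 2 range was 0 to 662 nM.

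The Vehicle-1.5% BID group mean is too low by about f/2. That assumes both samples are available and that early- and late-rescued participants have similar on-drug concentrations. Because f is unknown, the size of the group error cannot be stated more closely. The primary and key secondary analyses are untouched, and no hypothesis test uses Cmin,ss. It is still worth correcting, because the direction of the error is foreseeable and the remedy is small.

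**What to change.** In SAP 7.7, derive Cmin,ss by participant within actual treatment period. Use only preapplication samples taken on ruxolitinib cream after the documents' own time to steady state, for example at least 4 weeks after rescue starts, the upper end of the stated 2 to 4 weeks. Summarise vehicle-period samples separately under vehicle. State whether the Week 104 sample counts as preapplication. Align Protocol 10.4.3, or record the departure in SAP 10.1.

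The cost is a sentence or two and a filter on rescue start date, with no new data. A few participants would contribute one sample instead of two. Anyone rescued less than 4 weeks before Week 104 would contribute none to Cmin,ss, but would remain in the summaries by visit.

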8. SAFETY AND TOLERABILITY

Appendix A provides a list of planned tables, figures, and listings. Sample data displays are included in a separate document.

8.1. General Considerations

The analyses in this section will be provided for the FAS population for each cohort. Safety data for each cohort will be summarized in separate tables.

For AEs, summary tables will be provided based on the actual treatment received as defined in Section 5.2.

For laboratory tests and vital signs, summary tables will be provided based on the actual treatment received at Week 52. For Cohort A, only assessments on or before the first dose date of open-label rescue treatment will be summarized.

Also, for safety evaluations, baseline will be defined as stated in Section 4.1.3.

Summary tables may be replaced with listings when appropriate. For instance, an AE frequency table may be replaced with a listing if it only contains a few unique PTs reported on relatively few participants.

8.2. Adverse Events

8.2.1. Adverse Event Definitions

A TEAE is any AE either reported for the first time or worsening of a pre-existing event after first application of study drug in Study INCB 18424-308 and within 30 days of the last dose of study drug. For participants who cross over treatments, the first application date is treatment-specific, and the end date is 30 days after the last application date of this treatment, or the first application date in the next treatment, whichever comes first. Analysis of AEs (as discussed below) will be limited to TEAEs, but data listings will include all AEs regardless of their timing in relation to study drug application.

Adverse events will be tabulated by MedDRA PT and SOC. Severity of AEs will be graded using the National Cancer Institute CTCAE v5.0. The CTCAE reporting guidelines and grading details are available on the Cancer Therapy Evaluation Program website.

The subset of AEs considered by the investigator to be related to study drug will be considered to be treatment-related AEs. If the investigator does not specify the relationship of the AE to study drug, the AE will be considered to be treatment-related. The incidence of AEs and treatment-related AEs will be tabulated. Serious AEs will also be tabulated.

Any missing onset date, causality, or severity must be queried for resolution. Unresolved missing causality and severity will be handled according to the following rules:

- An unresolved missing causality will be considered treatment-related.
- An unresolved missing severity will be identified as an unknown severity.

For purposes of analysis, all AEs will be considered TEAEs unless the AE can unequivocally be defined as not treatment-emergent.

Application site reactions are AEs that occur at the site of drug application. A summary of ASRs will be provided.

8.2.2. Adverse Events of Interest

Adverse events of interest will be summarized in the following categories:

- Cytopenias
 - Anemia
 - Thrombocytopenia
 - Neutropenia
- Herpes zoster
- Viral skin infections
- Skin neoplasms
- Venous and arterial thromboembolic events
- Thrombocytosis and elevated mean platelet volume
- Liver function test elevations

8.2.3. Adverse Event Summaries

An overall summary of AEs by treatment groups (as defined in Section 4.2) will be summarized separately for each cohort and will include the following:

- Number (%) of participants reporting any TEAEs
- Number (%) of participants reporting any ASRs
- Number (%) of participants reporting any serious TEAEs
- Number (%) of participants reporting any Grade 3 or higher TEAEs
- Number (%) of participants reporting any treatment-related TEAEs
- Number (%) of participants who temporarily interrupted study drug because of TEAEs
- Number (%) of participants who permanently discontinued study drug because of TEAEs
- Number (%) of participants who had a fatal TEAE

The following summaries will be produced by MedDRA term (if 2 or fewer participants appear in a table, a listing may be appropriate):

- Summary of TEAEs by SOC and PT
- Summary of TEAEs by PT in decreasing order of frequency
- Summary of exposure-adjusted incidence rates of TEAEs by PT in decreasing order of frequency (Cohort A only)
- Summary of Grade 3 or higher AEs by SOC and PT
- Summary of Grade 3 or higher AEs by PT in decreasing order of frequency
- Summary of serious TEAEs by SOC and PT
- Summary of serious TEAEs by PT in decreasing order of frequency
- Summary of ASRs by SOC and PT
- Summary of ASRs by PT in decreasing order of frequency
- Summary of exposure-adjusted incidence rates of ASRs by PT in decreasing order of frequency (Cohort A only)
- Summary of treatment-related TEAEs by SOC and PT
- Summary of treatment-related TEAEs by PT in decreasing order of frequency
- Summary of Grade 3 or higher treatment-related TEAEs by SOC and PT
- Summary of treatment-related serious TEAEs by SOC and PT
- Summary of TEAEs with a fatal outcome by SOC and PT
- Summary of TEAEs leading to dose interruption of study drug by SOC and PT
- Summary of TEAEs leading to discontinuation of study drug by SOC and PT
- Summary of AEs of interest by PT in decreasing order of frequency

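### In Cohort A, the overall AE summary lines and the AE-of-interest category totals have no exposure-adjusted rate, although vehicle AE time stops at rescue and will be shorter than ruxolitinib time if relapse is more frequent on vehicle.

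*SAP*

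**What the plan says.** SAP 5.2 defines the groups: "For Cohort A, treatment groups are ruxolitinib cream 1.5% BID and vehicle cream for participants before open-label rescue treatment". It continues: "For participants who cross over from vehicle cream to open-label ruxolitinib cream, the treatment group will be Vehicle-1.5% BID". SAP 8.1 carries these groups into the safety tables: "For AEs, summary tables will be provided based on the actual treatment received as defined in Section 5.2". SAP 8.2.1 ends the TEAE window of a participant who crosses over at "30 days after the last application date of this treatment, or the first application date in the next treatment, whichever comes first".

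Rescue follows loss of F-VASI75, which is also the primary endpoint event. It applies to any Cohort A participant, in either arm (Protocol 6.7).

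SAP 8.2.3 has an overall summary of eight lines, all as number and percentage of participants: any TEAE, application site reactions, serious, Grade 3 or higher, treatment-related, interruption, discontinuation and fatal. Among the by-term summaries, two are exposure-adjusted, both for Cohort A only: "Summary of exposure-adjusted incidence rates of TEAEs by PT in decreasing order of frequency (Cohort A only"), and the matching summary of application site reactions by PT. Appendix A agrees (Tables 3.2.3.2 and 3.2.9.2). AEs of interest appear as "Summary of AEs of interest by PT in decreasing order of frequency", with no adjusted version, although SAP 8.2.2 says they will be summarized in categories such as cytopenias, skin neoplasms and thromboembolic events.

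**The concern.** A crude percentage mixes the event rate with the length of the window in which events are counted. A randomized withdrawal design expects more relapse, and so more rescue, on vehicle. The better ruxolitinib maintains response, the shorter the vehicle window becomes, and the higher the crude ruxolitinib percentage stands against vehicle even when the true rates are equal. The post-rescue group has the same problem, because it holds only the time left after rescue.

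The Cohort A rate tables suggest that the SAP recognizes unequal exposure there. They do not separate events by seriousness, grade, causality or discontinuation, and they give no category totals. A reader of the overall summary, Table 3.2.1.1, will see adjacent percentages from windows of different length. Safety and tolerability is a stated secondary objective, so those percentages are likely to be quoted.

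**Working it through.** The documents give no relapse rate, AE rate or figure to reproduce here. The check asks what the crude percentages would be if the true AE rate were the same in both arms.

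**Inputs from the documents**
- Treatment period of 52 weeks (Protocol Table 2).
- Clinic visits 4, 8, 12, 16, 28, 40 and 52 weeks after the Week 52 randomization (Protocol Table 3).
- TEAE window closing at rescue, or otherwise 30 days after last application (SAP 8.2.1). The full window is 52 + 30/7 = 56.3 weeks.

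**Assumptions, not in the documents**
- 52-week relapse of 20%, 40% or 60% on vehicle and 5% or 15% on ruxolitinib, with a constant hazard.
- Relapse found at the next scheduled visit, with rescue starting then. Relapse first found at Week 104 leaves no rescue period, so the full window applies.
- AE rate of 5 per 100 person-years in both arms, independent of relapse.
- No other dropout.

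**Formulas**
- Weekly relapse hazard h = -ln(1 - R)/52, where R is 52-week relapse.
- P(rescue at visit k) = exp(-h × previous visit) - exp(-h × visit k).
- Weekly AE hazard λ = 0.05/52.18.
- Crude percentage = Σ P(T) × (1 - exp(-λT)) over window lengths T.

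**Vehicle arm with 40% relapse** (h = 0.00982)

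| Window T (weeks) | P(T) | 1 - exp(-λT) | Product |
|---|---|---|---|
| 4 | 3.85% | 0.38% | 0.015% |
| 8 | 3.70% | 0.76% | 0.028% |
| 12 | 3.56% | 1.14% | 0.041% |
| 16 | 3.42% | 1.52% | 0.052% |
| 28 | 9.50% | 2.65% | 0.252% |
| 40 | 8.45% | 3.76% | 0.318% |
| 56.3 | 67.51% | 5.25% | 3.544% |
| Sum | 100% | | 4.25% |

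The mean window is 45.5 weeks. With 5% relapse on ruxolitinib, also stopped at rescue, the mean window is 55.0 weeks and the crude percentage 5.14%. The ratio is 5.14/4.25 = 1.21.

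**Across the assumed range** (ruxolitinib relapse 5%; last column without any stop at rescue)

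| Vehicle relapse | Mean window, vehicle vs ruxolitinib (weeks) | Crude, vehicle vs ruxolitinib | Ratio, both arms stopped | Ratio, only vehicle stopped |
|---|---|---|---|---|
| 20% | 51.2 vs 55.0 | 4.78% vs 5.14% | 1.08 | 1.10 |
| 40% | 45.5 vs 55.0 | 4.25% vs 5.14% | 1.21 | 1.24 |
| 60% | 38.9 vs 55.0 | 3.64% vs 5.14% | 1.41 | 1.44 |

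**Sensitivity**
- With 15% relapse on ruxolitinib and both arms stopped, the ratios are 1.03, 1.15 and 1.35.
- Over AE rates of 2 to 10 per 100 person-years, the range is 1.03 to 1.41 with both arms stopped and 1.10 to 1.45 with only vehicle stopped.
- For a common AE (60 per 100 person-years), the range over all scenarios is 1.02 to 1.39.
- With equal relapse and both arms stopped, the ratio is 1.00. With equal relapse of 30% and only vehicle stopped, it is 1.16.

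**The same data as first-event rates.** Expected time at risk is Σ P(T) × (1 - exp(-λT))/λ. At 40% vehicle relapse this is 0.850 person-years on vehicle and 1.027 on ruxolitinib. The rates are 0.0425/0.850 and 0.0514/1.027, both 5.0 per 100 person-years, so the ratio is 1.00.

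**The case against.** The strongest reply is that the SAP already covers much of this. AEs of interest are tabulated by PT, and Table 3.2.3.2 gives an adjusted rate for every TEAE PT in Cohort A. A reader might infer that the AEs of interest are left wholly on a crude measure, and that would be wrong. The gap is at the level of category totals. It is still a gap, because first-event category rates cannot be obtained by adding PT rates: a participant with two PTs in a category would count twice.

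Second, a reader might infer that a biased between-group safety comparison is planned. None is. Protocol 10.3 confines formal tests to the primary and key secondary endpoints, SAP 3.2 calls all analyses exploratory, and SAP 6.4 reports exposure by actual treatment. This lowers the stakes, but total exposure does not give first-event rates by line or category.

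Third, the distortion is conditional. Rescue applies in both arms, and SAP 5.2 can be read as stopping both at rescue. With equal relapse the ratio is then 1.00. This stands, and it is why the size is given as a range.

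Fourth, the direction is against ruxolitinib, so the crude figures do not hide excess risk on ruxolitinib relative to vehicle. That also stands, though a misleading excess is still misleading.

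Finally, one might want a single column pooling all ruxolitinib time. SAP 8.1 keeps the cohorts apart: "Safety data for each cohort will be summarized in separate tables". The cohorts differ in Week 52 response and blinding, and safety baselines differ between groups (SAP 4.1.3). Not pooling is a defensible choice, not an error.

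**Conclusion.** The point holds in a limited form. Vehicle AE time in Cohort A is cut at rescue, the overall-summary lines are crude, and the AE-of-interest category totals have no adjusted rate. With equal true rates, both arms stopped at rescue and 5% relapse on ruxolitinib, the crude ratio is about 1.08 at 20% vehicle relapse and 1.41 at 60%. These relapse figures are assumptions. The result depends on unequal relapse or on stopping the clock in one arm only.

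The second possibility is a separate ambiguity. SAP 5.2 applies its pre-rescue wording to both arms but names a post-rescue group only for vehicle participants. It is therefore unclear whether blinded ruxolitinib followed by open-label ruxolitinib counts as a change of treatment under SAP 8.2.1. That affects the window and the denominator of every Cohort A rate, including the two already planned.

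**What to change.** 1. For Cohort A, add to Table 3.2.1.1 the number of participants with a first event per 100 person-years at risk, with 95% CI, for the overall-summary lines (at least serious, Grade 3 or higher and discontinuation TEAEs). Add the same to the AE-of-interest summary for each category in SAP 8.2.2.
2. State that any descriptive ruxolitinib-versus-vehicle safety statement rests on these rates, with the crude counts kept alongside.
3. In SAP 5.2, state whether ruxolitinib-arm AE time stops at rescue and, if so, which group the later time and events enter.
4. In SAP 8.2.3, correct the reference for treatment groups from Section 4.2, which defines BMI and concomitant medication, to Section 5.2.

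The cost is a few more first-event derivations and table columns. The exposure data are already needed for Tables 3.2.3.2 and 3.2.9.2, and no new data are collected.
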